ng/ml, the frequency of administration will be reduced to once a month. The participants will receive supplementation for a total of 6 months. At this time, vitamin D levels will be reassessed and participants will undergo follow-up functional assessments, and cognitive and immune testing. Subjects will be recruited from the outpatient hemodialysis (HD) unit which is located on the fourth floor of the James J. Peters VAMC.

Primary Outcomes (tested at Baseline, 3 months and 6 months):

- 1) Neuromuscular functional performance using the 50ft timed walk, the TUG, a timed stair climb, and the Chair Raise test, (48)
- 2) Postural stability using a Sway meter (NeuroCom International, Inc., Clackamas, OR) that measures displacement of the body at the level of the waist in 30 second periods (49) and the Functional Reach test.
- 3) Muscle hand grip strength using the Harpenden Hand Grip dynamometer (50) and hip flexor and knee extensor strength using a Push-Pull Muscle Strength dynamometer.

Secondary Outcomes:

- 1) Cognitive function (tested at Baseline, 3 and 6 months):
 - a) Mental Status: Mini-Mental Status Exam (MMSE) (51) and Short Blessed Test (SBT) (52);
 - b) Memory: California Verbal Learning Test – II (CVLT-II) (53);
 - c) Language: Category Fluency and Controlled Oral Word Association Test (COWAT) (54);
 - d) Attention and Processing Speed: Trails A (55), Digit Span (56), Symbol Digit Modality Test (SDMT) (57), and Stroop Color and Word (58)
 - e) Executive Function: Trails B (55) and Stroop Color-Word (58).
- 2) Self-assessment of Physical Fxn and Health (tested at Baseline, 3 months and 6 months):
 - a) Physical Activity Scale for Persons with Physical Disabilities (PASIPD) (59)
 - b) NIH PROMIS (v1.0 Item Banks): Global Health Physical Function, Pain, Fatigue, Sleep, Emotional Distress (60)
 - c) Beck Depression Inventory (BDI)
- 3) Immunology (tested at Baseline, 6 months)
 - a) Serum cytokines

This study will be performed over two years.

TABLE 1. Study Flow Sheet	BL 1	BL 2	Month 1	6 weeks	Month 2	Month 3	Month 4	Month 5	Month 6
Week:	0	0 ₂	4	6	8	12	16	20	24
Physical Function Assessment 50ft walk, TUG, stair climb, Chair Raise, Functional Reach, Sway, Hand Grip, Hip & Knee Strength		X				X			X
Self - Assessment PASIPD & NIH PROMIS (short forms): Physical Fxn, Pain, Fatigue, Global Health, Sleep, Emotional Distress, BDI		X				X			X
Cognitive Impairment Tests									

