Mental Status: Mini-Mental Status Exam (MMSE) (for screening), Short Blessed Test (SBT)		X							X
Executive Function: Trails B, STROOP Color-Word		X							X
Memory: California Verbal Learning Test (CVLT-II)		X							X
Attention & Processing Speed: Trails A, DS WAIS-III, SDMT, StroopColor, Stroop Word		X							X
Language: Category Fluency, Controlled Oral Word Association Test		X							X
Metabolic & Endocrine Tests	X	X	X	X	X	X	X	X	X
Vitamin D Monthly Renal Clinic labs (chart review) B12 Folate		X	X		X	X	X	X	X
Immune Function Tests serum cytokines		X							X
Demographic Data & Health Monitoring									
Age, Height, Weight, BMI, Co-morbidities, HD Hx (chart review)		X							X

Power analysis: We expect that vitamin D supplementation will improve muscular function and strength. Using information from the limited studies reported in the literature, Pfeifer, et al. (25) reported an 11% decrease in the timed up and go test for individuals treated with Vitamin D replacement therapy compared with placebo who had an average decrease. We believe our study subjects will respond in a similar manner and have powered our study such that we expect 15 of 20 subjects in the treatment group to achieve an 11% decrease in the TUG test, consistent with the Pfeifer, et. al. study findings. Similarly, postural sway has been reported by two different groups to decrease by 9% (24) and 28% (25). To be conservative, we have chosen an expected 15% decrease in postural sway in our study subjects. Muscle strength as measured by hip extensor has been reported to improve by 16% (26), and by knee extensor strength gains from 8% to 25% (25, 26). Therefore to be on the conservative side, we have

hypothesized a 10% muscle strength increase in hand grip and hip flexor strength. Only 1 of 10 in the placebo-control group is anticipated to demonstrate these improvements.

We estimate power for a two-sided test using a continuity correction. At an alpha of 0.05, with treatment response of 75% and placebo response of 10%, we estimate 90% power for a sample size of 26; 80% power with a sample size of 22 and 70% power for a sample size of 18. We are proposing a sample of 30 permitting 33% drop out to permit us to maintain reasonable power for a pilot study.

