The primary analysis for functional and cognitive outcomes will use the responder analysis described above. Additional secondary analyses will be performed on the primary outcome variables. In the first analysis, the percent change variables will be used for the group comparisons and analyzed by one-way analysis of variance (ANOVA) ($Y_1 = \%$ change; $X_1 = \text{Group}$). The percent change variable has the advantage of being easily analyzed in an analysis of covariance (ANCOVA) model if controlling variables are identified. For example, years on hemodialysis (HD y) may be need to be controlled for and as such this model would be $Y = \%$ change; $X_1(\text{HD y}) + X_2(\text{Group})$. The second analysis to be performed on the primary outcome variables will be the more traditional two-factor mixed model (2x3 table), where the between factor is Group (treatment, placebo) and the repeated measures (i.e. the within-subjects) factor is Time (BL, 3 and 6 months). In the case of missing data we will use 2 imputation methods. First as is commonly done in clinical trials of cognitive impairment and dementia we will use the last observation carried forward for missing terminal visits. We will compare results from these methods with a variety of other imputation methods. For missing data within a specific test, we will assign the average the remaining domains for those that do not complete a domain. Other imputations will include assigning values from 1) a regression across the available time points, and 2) assigning the average value of all subjects within in the group. We will compare results using these different imputations.

Significant main effects will further be explored by single degree of freedom post hoc analyses. For the secondary analyses covariates will be used including age and education adjusted T scores will be used for the baseline versus 6 month comparisons by performing a 2x2 repeated measures ANOVA. For

the self assessment variables (PASIPD and NIH PROMIS) percent change will be calculated as previously described and analyzed by one-way ANOVA as described for the primary outcome variables above.

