- 3) Muscle hand grip strength using the Harpenden Hand Grip dynamometer (50) and hip flexor and knee extensor strength using a Push-Pull Muscle Strength dynamometer.

Functional self-assessments (interview)

- 1) Self-assessment of Physical Fxn and Health:
 - a) Physical Activity Scale for Persons with Physical Disabilities (PASIPD) (59)
 - b) NIH PROMIS (v1.0 Item Banks): Global Health Physical Function, Pain, Fatigue, Sleep, Emotional Distress (60)
 - c) Beck Depression Inventory (BDI)

The following outcomes will be tested at **Baseline and 6 months**:

- 1) Cognitive function (as conducted through participant interview):

- a) Mental Status: Mini-Mental Status Exam (MMSE) (51) and Short Blessed Test (SBT) (52);
- b) Memory: California Verbal Learning Test – II (CVLT-II) (53);
- c) Language: Category Fluency and Controlled Oral Word Association Test (COWAT) (54);
- d) Attention and Processing Speed: Trails A (55), Digit Span (56), Symbol Digit Modality Test (SDMT) (57), and Stroop Color and Word (58)
- e) Executive Function: Trails B (55) and Stroop Color-Word (58).

- 2) Immunology (tested at Baseline, 6 months)
 - a) Serum cytokines

2. Provide description of these procedures. If pharmacologic agents or radioisotopes are to be administered, give dosages, mode of administration and duration of usage.

Vitamin D administration Following baseline testing, the treatment group will receive 50,000 IU (standard replacement therapy) of oral cholecalciferol or placebo. The initial dose of cholecalciferol will be 50,000 IU weekly for 6 weeks. Vitamin D levels will then be measured. Participants who still have Vitamin D insufficiency (≤ 35 ng/ml) will remain on 50,000 IU of cholecalciferol for another 6 weeks, at which point Vitamin D levels will be measured again. Participants who reach 25-OH levels > 35 ng/ml will have their dosing regimen lessened to 10,000 IU weekly (maintenance dose) for the remainder of the 6 months. Participants receiving placebo will start taking the placebo maintenance dose after the first 6 weeks. 25(OH) vitamin D₃ levels will also be re-measured at monthly intervals and followed by an independent medical monitor. In patients who have serum vitamin D levels ≥ 60 ng/ml, the frequency of administration will be reduced to once a month. The participants will receive supplementation for a total of 6 months.

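### Cognition is scheduled at three visits in one place and two elsewhere; on the two-visit schedule, carrying the last observation forward gives every participant missing month 6 zero change.

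*Combined protocol and SAP*

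**What the plan says.** Four places in the combined document bear on the cognitive schedule.

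- **Section C, Secondary Outcomes, item 1:** "Cognitive function (tested at Baseline, 3 and 6 months".
- **Table 1 (Study Flow Sheet):** all five cognitive rows, for example "Memory: California Verbal Learning Test (CVLT-II", are marked at the second baseline visit and Month 6 only. The physical-function and self-assessment rows in the same table also carry a Month 3 mark.
- **Section C.a.1:** "Cognitive function (as conducted through participant interview" is item 1 under the heading "The following outcomes will be tested at Baseline and 6 months", apart from the outcomes listed there for three time points.
- **Statistical Analysis Plan:** the secondary analyses use age- and education-adjusted T scores for "baseline versus 6 month comparisons by performing a 2x2 repeated measures ANOVA", whereas the primary outcomes get a 2x3 model.

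On missing data, the Statistical Analysis Plan says "we will use the last observation carried forward for missing terminal visits" and justifies this by practice in cognitive impairment and dementia trials. It adds "a regression across the available time points" and a group-average imputation, and says that the results will be compared. The same section makes the responder analysis primary for cognitive as well as functional outcomes.

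**The concern.** Staff working from the Secondary Outcomes list would give a full cognitive battery at month 3. Staff working from Table 1 would not. The schedule also decides what the missing-data rules do. With a month 3 test, LOCF carries a post-treatment value for anyone who leaves after it, and that person has two points for a regression. Without it, the only value before month 6 is baseline. The imputed result is then no change by construction, whatever happened to the participant. Specific aim 2 rests on these tests, and the plan says that improvement in neuromuscular and/or cognitive function would lead to immediate use in practice.

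**Working it through.** **1. Schedule.** One place has three visits; Table 1, section C.a.1 and the 2x2 analysis have two. A lost table mark is unlikely to explain this, because neighbouring rows kept their Month 3 mark and section C.a.1 separately places cognition under a two-visit heading.

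**2. LOCF with two visits.** Change = (baseline − baseline) / baseline × 100 = 0%. This is a non-response under any threshold that requires improvement.

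**3. Mean effect.** If a fraction d of each arm is set to zero change, and those who leave would have responded like those who stay, the difference becomes (1 − d) × (treatment mean − placebo mean). At d = 1/3 it shrinks by one third.

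**4. Regression.** A line fitted to one participant's own visits has two parameters. With baseline alone the design matrix has rank 1, so there is no unique solution. With baseline and month 3 the rank is 2. Group-mean imputation needs only the observed month 6 values and can still be computed.

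**5. The plan's own power figures.** These are for the physical outcomes: 75% against 10%, two-sided alpha 0.05, continuity-corrected; stated power 90%, 80% and 70% at totals of 26, 22 and 18. The normal-approximation formula gives 90.7%, 82.1% and 68.0% at 1:1 allocation, and 85.9%, 74.7% and 58.2% at the planned 2:1. The stated figures therefore match 1:1. That is a separate matter; the steps below use the planned 20 against 10.

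**6. Illustration on the responder scale.** Assumptions: the 75% and 10% rates are borrowed from the physical outcomes, and dropout is equal by arm. One third is the plan's dropout allowance (10 of 30), not a forecast.

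LOCF multiplies each rate by (1 − d) and keeps 20 against 10. Complete cases keep the rates and lose the people. Power is the sum of binomial probabilities over all outcomes (a, b) for which

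(|a/n1 − b/n2| − ½(1/n1 + 1/n2)) / √[p̄(1 − p̄)(1/n1 + 1/n2)] ≥ 1.96, where p̄ = (a + b)/(n1 + n2).

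| Dropout | Rates after LOCF | Power, LOCF (20 vs 10) | Power, complete cases |
|---|---|---|---|
| 0 | 75% vs 10% | 92.1% | 92.1% (20 vs 10) |
| 10% | 67.5% vs 9.0% | 84.3% | 88.9% (18 vs 9) |
| 20% | 60% vs 8% | 73.6% | 80.4% (16 vs 8) |
| One third | 50% vs 6.7% | 53.0% | 69.9% (13 vs 7) |

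At one third the cost of LOCF itself is 69.9 − 53.0 = 16.9 points. With Fisher's exact test it is 72.8 − 65.3 = 7.5 points. The split matters at this size: 14 against 6 completers gives 66.7% (Fisher 80.2%), so these gaps are approximate.

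**7. Unequal dropout.** With 20% lost on vitamin D and 40% on placebo, the LOCF difference is 0.75 × 0.8 − 0.10 × 0.6 = 54 points. With the fractions reversed it is 0.75 × 0.6 − 0.10 × 0.8 = 37 points. Without dropout it is 65.

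**The case against.** Cognition is a secondary outcome that the plan calls exploratory, in a pilot of 30. LOCF is one of several methods to be compared, and group-mean imputation does not force zero change. The regression wording does not say within-participant; a regression of month 6 on baseline across participants could be fitted. The LOCF sentence follows the primary-outcome models, so it might be meant for those alone.

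Much of this stands. It limits the importance of the point and rules out saying that the missing-data plan cannot be carried out. It does not remove the problem. LOCF is named first, its justification refers to cognitive trials, and no other rule is given for a missed cognitive visit. A cross-participant regression is not described, so at best the model is unspecified.

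A reader might go further in three ways that the documents do not support.

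- **That LOCF takes power from 92% to 53%.** That comparison charges LOCF with the loss of people, which any method suffers. The like-for-like figure at one-third dropout is about 70% against 53%.
- **That the planned handling removes the effect.** It shrinks it; 50% against 6.7% is left in the illustration.
- **That the conflict over month 3 biases the arms through practice effects.** If one schedule is applied to everyone, both randomised arms have the same test exposure. No between-arm bias follows.

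**Conclusion.** The schedule contradiction is established from the text. On the two-visit schedule it is also certain that LOCF gives zero change and non-response to everyone missing month 6, and that a within-participant regression has no unique solution for them. A mean effect shrinks by the dropout fraction if dropout is equal by arm and leavers would have responded like completers.

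The power figures are illustrative only, because the plan states no cognitive responder threshold or rates. On borrowed rates and equal dropout, LOCF costs about 17 points at one-third dropout with the continuity-corrected test, about 8 with Fisher's test, and less at lower dropout with the continuity-corrected test. This should be corrected, but it does not threaten the primary physical outcomes.

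**What to change.** 1. Change the Secondary Outcomes entry for cognition to baseline and 6 months, to match Table 1, section C.a.1 and the 2x2 analysis. Keeping month 3 instead would help the imputation rules only for those who leave after that visit. It would add a test session and require changes in the other three places.
2. For cognition, drop LOCF and the within-participant regression imputation. Analyse observed 6-month scores by ANCOVA adjusted for baseline.
3. State the cognitive responder threshold. Run the responder analysis, which the plan makes primary, on participants with an observed month 6 score.
4. Use multiple imputation by arm (baseline score, age, education) as sensitivity for both analyses. Report missing-as-non-responder only as a labelled sensitivity analysis.

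The cost is protocol and SAP wording, with no added visit. The downside is a smaller analysed sample and the assumption that data are missing at random given baseline. The unadjusted responder comparison needs the stronger assumption that, within each arm, leaving is unrelated to response. With about seven placebo completers at one-third dropout, an imputation model with three predictors fitted by arm would be thin. The change removes the built-in shrinkage; it does not restore the 92% power of a trial without dropout.

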(24). In a 20 month trial, vitamin D supplementation with calcium, versus calcium alone significantly improved body sway by 28% and decreased the time needed to perform time up and go test by 11% in those with 25-(OH) vitamin D levels < 31 ng/ml (25). In another randomized controlled clinical trial patients received 6 months of calcium and vitamin D (150,000 units/month for the first two months, followed by 90,000 units/month for the last 4 months) or calcium and placebo to determine the effect on lower limb muscle strength (26). At 6 months, the group on placebo showed no change in knee extensor or hip flexor strength while the group on vitamin D arm showed a significant increase in hip flexor of 16% and a significant increase of 24% in knee extensor strength. Further studies are required to determine the optimal dose of 25-(OH) vitamin D to attain optimal muscle performance and strength.

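### The 75% TUG response rate behind the power statement does not follow from the cited trial's 11% group effect, and power is shown for that rate only

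*Combined protocol and SAP*

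**What the plan says.** The background section on muscular function and cognition describes a 20-month trial that gave vitamin D plus calcium to people with 25-OH vitamin D below 31 ng/ml. Its finding is reported this way: "versus calcium alone significantly improved body sway by 28% and decreased the time needed to perform time up and go test by 11" (per cent). This is a result for the group.

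The Power analysis repeats the 11% figure and describes it as a "decrease in the timed up and go test for individuals treated with Vitamin D replacement therapy compared with placebo who had an average decrease". No number is given for the placebo change. The next sentence turns 11% into a cut-off for the individual patient: "we expect 15 of 20 subjects in the treatment group to achieve an 11% decrease in the TUG test", described as agreeing with the cited trial. One in 10 placebo patients is expected to respond.

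Power is then given for that one pair of rates: "with treatment response of 75% and placebo response of 10%, we estimate 90% power for a sample size of 26", with 80% at 22 and 70% at 18. The sample size varies; the response rates do not. The plan proposes 30 patients, randomised 20:10, and allows for 33% drop-out.

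The Statistical Analysis Plan relies on the same cut-offs: "The primary analysis for functional and cognitive outcomes will use the responder analysis described above".

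**The concern.** A mean change and the share of patients who reach that mean are different quantities. Going from one to the other requires the spread and shape of the individual changes, and the documents give neither. If changes are symmetric around the mean, half the patients lie on each side of it, so an 11% mean fall gives about 50% responders.

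The 75% rate is an input to the power of the primary responder analysis. If the true TUG response is nearer 50%, the cited effect could be fully present and the responder comparison could still quite easily miss it. A reader of the Power analysis cannot see this, because 75% appears as something the literature supports and no other rate is shown.

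**Working it through.** **Inputs from the documents.** Treated response 15/20 = 0.75; placebo response 1/10 = 0.10; two-sided alpha 0.05 with continuity correction; planned arms 20 and 10; drop-out 33% (all in the Power analysis and in Research Design and Methods). The SDs and the normal model used below are assumptions.

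**Formula.** Power = Φ[(d − c − 1.96·SE0)/SE1], where d = p2 − p1, c = 0.5(1/n1 + 1/n2), SE0 uses the pooled proportion and SE1 the separate proportions.

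**Reproducing the plan.** For 0.75 v 0.10 at 13:13, d = 0.65, c = 0.077, SE0 = 0.194 and SE1 = 0.146. Then (0.65 − 0.077 − 1.96 × 0.194)/0.146 ≈ 1.32, so power is 90.7%. The plan states 90% at 26. The same formula gives 82.1% at 22 and 68.0% at 18 (stated 80% and 70%). These matches are under equal allocation. The planned ratio is 2:1, so the figures below use 20:10.

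**From a mean to a response rate.** With normal changes, P(fall ≥ 11) = Φ[(mean − 11)/SD]. A mean of 11 gives Φ(0) = 50% at any SD. For 75%, the mean must be 11 + 0.674·SD: 14.4% at SD 5, 17.7% at SD 10.

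**Varying the treated response** (20:10, placebo 10%, all 30 analysed). Example at 50%: d = 0.40, c = 0.075, SE0 = 0.187, SE1 = 0.147; (0.40 − 0.075 − 1.96 × 0.187)/0.147 ≈ −0.28, so power is 39%.

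| Treated response | Plan's formula | Exact, Yates | Exact, Fisher |
|---|---|---|---|
| 50% | 39% | 43% | 54% |
| 55% | 51% | 56% | 65% |
| 60% | 63% | 68% | 74% |
| 65% | 75% | 78% | 81% |
| 70% | 85% | 86% | 87% |
| 75% | 93% | 92% | 93% |

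**With drop-out.** 30 × 2/3 = 20 patients, about 13:7. The plan's formula gives 20% at 50% response and 69% at 75%. This assumes that those who drop out are not analysed.

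**Letting placebo response move with the SD.** Take a mean fall of 11% on vitamin D and 0 on placebo, normal with equal SDs, 20:10. Treated response is 50% throughout; placebo response is Φ(−11/SD).

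| Assumed SD | Placebo response | Power |
|---|---|---|
| 5 | 1.4% | 67% |
| 8.6 | 10% | 39% |
| 15 | 23% | 15% |

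**Can 75% v 10% arise from an 11% effect?** Yes, if 11% is the difference between arms. The treated mean must lie 0.674·SD above the cut-off and the placebo mean 1.282·SD below it, so 11 = 1.956·SD. That gives SD ≈ 5.6, a placebo fall of 11 − 1.282 × 5.62 ≈ 3.8% and a treated fall of about 14.8%.

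**The case against.** **The 75% rate may be right.** The last calculation shows a plausible route to it. The plan also has a reason to expect a larger effect than in the cited population. Entry requires a level below 25 ng/ml, chosen because improvement is said to be greatest below it. The background reports most of the functional gain between 9 and 16 ng/ml, and the local preliminary mean was 12.86 ng/ml. This stands as a reason for optimism. It does not supply a rate: the plan turns none of it into a responder proportion, and its follow-up is 6 months against 20.

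**The reference to the cited trial may cover only the 11%, not the 15 of 20.** The sentence can be read that way. The 75% then has no stated source at all, and the remedy is the same.

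**50% and 39% are assumptions too.** Correct. A reader might infer that true power is 39%, or that 39–93% is the full range. The documents support neither. The figures hold only with placebo response at 10% and 30 analysed patients, and the SD table gives values on both sides of 39%.

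**This is a pilot, and TUG is one of several primary measures.** That limits the consequence. H1 names postural sway, and a comparison in which "the percent change variables will be used for the group comparisons and analyzed by one-way analysis of variance" is already planned as a secondary analysis. A reader might infer that the trial needs more patients or a different primary analysis; nothing here shows that. The plan does, however, state formal power, and the statement rests on this rate.

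**Extending the point to sway.** A reader might also fault "To be conservative, we have chosen an expected 15% decrease in postural sway in our study subjects", since one cited effect is 9%. That effect was seen within 8 weeks and the other, 28%, at 20 months. A 15% figure lies between them, so the wording is arguable and not an error.

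**Conclusion.** The point holds for TUG. A 75% treated response is an assumption and does not follow from an 11% group effect; the documents contain nothing that would turn one into the other. It is neither impossible nor shown to be wrong.

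The stated power is sensitive to it. Each 5-point drop in treated response from 75% costs roughly 8 to 12 points of power, ending at about 39% when half the treated patients respond. Exact tests show the same decline, to 43% (Yates) or 54% (Fisher). These figures rest on a 10% placebo response and complete data, and the 50% case rests on symmetric changes around an 11% mean. The true response rate, and so the true power, cannot be fixed from the documents. This should be corrected because the rate feeds the power statement for the primary responder analysis.

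**What to change.** In the Power analysis:

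1. State that the 75% treated response is an assumption of this plan and not a result of the cited trial. If a responder proportion or an SD is available to support it, give it.
2. Give TUG responder power as conditional on the response rates. For the plan's two-sided continuity-corrected test at 20:10, with placebo response 10% and all 30 analysed: about 39, 51, 63, 75, 85 and 93% at treated responses of 50, 55, 60, 65, 70 and 75%. With 33% drop-out (about 13:7): about 20% at 50% and 69% at 75%.
3. Add that 39% is not a floor, because placebo response also varies with the unknown SD. For a mean fall of 11% against 0 under a normal model, power is about 67% at an assumed SD of 5, 39% at 8.6 and 15% at 15.

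This takes a few sentences and no new data. Sample size, primary analysis and hypotheses do not change. The cost is that the plan must show a less favourable power than it now states.

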We propose to perform a prospective, randomized, double-blind placebo controlled trial. Patients will be included if they are: 1) receiving outpatient hemodialysis at the James J. Peters VAMC, 2) receiving IV vitamin D therapy according to National Kidney Foundation guidelines, 3) between the ages of 45-89 years, 4) a veteran outpatient or stable community living center patient, and 5) able to ambulate independently or with an assistive device for at least 20 feet. Exclusion criteria include: 1) 25-OH vitamin D level \geq 25 ng/ml, 2) hypercalcemia, 3) active malignancy within 6 months, 4) receiving intravenous antibiotics for infection, 5) history of dementia, 6) hemoglobin $<$ 8.5g, 7) history of conditions that interfere with postural instability (e.g. cerebellar disease, vestibular disease or any others that may present), and 8) poor compliance with dialysis treatments (history of skipping \geq 2 treatments per month for $>$ 2 months). A 25-OH vitamin D level of $<$ 25 ng/ml level was chosen based on previous studies that have shown that patients have the greatest improvement in muscle strength when levels below this threshold are increased. Patients will first be identified based on the inclusion criteria, then informed about the study and consented. Those who meet the exclusion criteria will be randomized to treatment or placebo. Enrolled participants will be randomized 2:1 to receive vitamin D (n=20) or placebo (n=10) for 6 months. All participants will be tested twice over two weeks to establish baseline values. Following baseline testing, the treatment group will receive 50,000 IU (standard replacement therapy) of oral cholecalciferol or placebo. The initial dose of cholecalciferol will be 50,000 IU weekly for 6 weeks. Vitamin D levels will then be measured. Participants who still have Vitamin D insufficiency (\leq 35 ng/ml) will remain on 50,000 IU of cholecalciferol for another 6 weeks, at which point Vitamin D levels will be measured again. Participants who reach 25-OH levels $>$ 35 ng/ml will have their dosing regimen lessened to 10,000 IU weekly (maintenance dose) for the remainder of the 6 months. Participants receiving placebo will start taking the placebo maintenance dose after the first 6 weeks. For safety monitoring, 25(OH) vitamin D₃ levels will also be re-measured at monthly intervals and followed by an independent medical monitor. In patients who have serum vitamin D levels \geq 60

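### The primary responder analysis names no test. The only one described, a continuity-corrected test, is valid but conservative: against Boschloo's exact test it costs about 4 points of power with all 30 analysed and 15 to 19 with 18 to 20

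*Combined protocol and SAP*

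**What the plan says.** Under Research Design and Methods in section C, "Enrolled participants will be randomized 2:1 to receive vitamin D (n=20) or placebo (n=10) for 6 months".

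The Power analysis paragraph states: "We estimate power for a two-sided test using a continuity correction. At an alpha of 0.05, with treatment response of 75% and placebo response of"; the figure assumed for placebo is 10%. The results are "we estimate 90% power for a sample size of 26" and "80% power with a sample size of 22 and 70% power for a sample size of 18". It then says "We are proposing a sample of 30 permitting 33% drop out".

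The Statistical Analysis Plan paragraphs say: "The primary analysis for functional and cognitive outcomes will use the responder analysis described above". No test is named there. ANOVA, ANCOVA and the two-factor mixed model are labelled secondary. Missing terminal visits are handled by last observation carried forward, with other imputations for comparison. No exact test is mentioned anywhere.

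**The concern.** An analyst who follows the reference back finds one test only, the two-sided continuity-corrected comparison of two proportions at 0.05. In groups of 20 and 10 or smaller, the correction keeps the true error rate well below 5%, and the unused part is given up as power. A pilot of 30 that allows for a third dropping out has little power to spare. A difference of the assumed size could be called non-significant because of the chosen statistic rather than because the data are too few.

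**Working it through.** **Inputs.** Alpha 0.05 two-sided, 75% v 10%, and totals of 26, 22 and 18 come from the Power analysis. The 20:10 allocation comes from Research Design and Methods. A 33% drop-out leaves 30 × 2/3 = 20, about 13:7. Assumption: losses keep roughly the 2:1 ratio.

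**1. The plan's own figures.** With d = 0.65, continuity-corrected power is Φ(z), where

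z = [d − ½(1/n₁ + 1/n₂) − 1.96·√(p̄(1 − p̄)(1/n₁ + 1/n₂))] / √(p₁(1 − p₁)/n₁ + p₂(1 − p₂)/n₂).

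At 13:13, p̄ = 0.425 and z = (0.65 − 0.077 − 0.380)/0.146 = 1.32, giving 90.7%. At 11:11 it gives 82.1% and at 9:9 it gives 68.0%. The printed 90/80/70% therefore fit this test at 1:1 allocation. At 2:1 the same formula gives 85.9%, 74.7% and 58.2% for totals of 26, 22 and 18, and 92.6% at 20:10. That mismatch is a separate point.

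**2. Exact behaviour of the corrected test.** Every possible 2×2 table was enumerated. With cells a, b (treated responders and non-responders) and c, d (the same for placebo), N the total and m the number of responders, the test rejects when

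N(|ad − bc| − N/2)² / [n₁n₂m(N − m)] ≥ 3.84 (correction floored at zero).

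Size is the rejection probability when both arms share one response rate, maximised over that rate. Power is the sum of Bin(n₁, 0.75) × Bin(n₂, 0.10) over the rejection region.

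**3. Comparison with Boschloo's test.** This orders tables by the Fisher p-value and controls the error over all common rates. Two conventions were run: (A) two one-sided tests at 2.5% each, and (B) ordering by the two-sided Fisher p-value.

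| n₁:n₂ | Max size, corrected | Max size, Boschloo A | Power, corrected | Power, Boschloo A (B) | Gain, points |
|---|---|---|---|---|---|
| 20:10 | 2.1% | 4.3% | 92.1% | 96.1% (95.8%) | about 4 |
| 17:9 | 1.5% | 4.1% | 84.7% | 92.8% (91.9%) | 7–8 |
| 15:7 | 1.3% | 3.7% | 73.8% | 85.6% (85.6%) | about 12 |
| 13:7 | 1.3% | 4.2% | 69.9% | 84.6% (84.6%) | about 15 |
| 12:6 | 1.2% | 4.3% | 60.2% | 79.3% (77.2%) | 17–19 |

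**4. One table by hand.** Take 9 of 13 v 1 of 7. Here ad − bc = 9×6 − 4×1 = 50, and the statistic is 20 × (50 − 10)² / (13 × 7 × 10 × 10) = 32,000/9,100 = 3.52, not significant. With 10 of 13 it is 20 × (57 − 10)² / (13 × 7 × 11 × 9) = 44,180/9,009 = 4.90, significant. Boschloo's test already rejects at 9. With no placebo responders the thresholds are 8 (corrected) and 6 (Boschloo).

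**5. Weaker effect, all 30 analysed.** At an assumed 50% v 10%, power at 20:10 is 43.3% for the corrected test and 60.6% for Boschloo A (56.0% for B), a gain of 17 (13) points.

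**6. Other candidates.** Fisher's exact test recovers little at 13:7 (72.8%), though more at 12:6 (74.8%). The uncorrected Pearson test exceeds 5% (maximum 5.2% at 20:10, 6.7% at 12:6).

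**7. Independence from allocation.** At 1:1 the corrected test is still conservative: maximum size is 2.9%, 1.7% and 1.0% at 13:13, 11:11 and 9:9.

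**The case against.** - **The test is named for power, not analysis.** This stands. A reader might infer that the plan prescribes the corrected test for its primary analysis. The text supports only that the analysis refers back to a section where no other test appears. If the sponsor meant another test, then none is specified, and the remedy is still to name one.
- **The loss at the planned size is small.** This also stands. With all 30 analysed at 75% v 10% the corrected test has 92% power, and the plan's expected result (15 of 20 v 1 of 10) is significant with it. A reader might take 15 to 19 points as the cost of the plan as it stands. Those figures need only 18 to 20 analysed patients, whereas the plan carries last observations forward and measures the primary outcomes at 3 months. Carrying forward does not remove the issue, however. If a third drop out and all of them count as non-responders (assumed rates 75% × 2/3 = 50% and 10% × 2/3 = 6.7%), power at 20:10 is 53% against 66–71% with Boschloo's test.
- **Every valid test is conservative in small discrete samples.** True. If both arms respond at 10%, the corrected test runs at 0.25% (20:10), 0.08% (13:7) and 0.50% (12:6). Boschloo A is also far below 5%, at 1.3%, 0.8% and 0.55%. A reader might infer a type I error defect, but there is none; the cost is power only.
- **The shortfall against the printed 90/80/70% comes from the correction.** A reader might infer this, but it is largely the 1:1 v 2:1 mismatch. At 1:1 the corrected test's exact power is 93.5%, 83.9% and 65.7% at totals of 26, 22 and 18.
- **Conservatism gives some protection across endpoints.** In part. The plan lists nine primary measures with no multiplicity rule. If all nine were independent and at maximum size for 20:10, the chance of any false positive would be 1 − (1 − 0.0205)⁹ = 17% with the corrected test and 1 − (1 − 0.0428)⁹ = 33% with Boschloo A. Nor does the low size per test mean an overall error of 1–2%. An accidentally conservative test is no substitute for a rule, but this is a real downside of the change.

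**Conclusion.** The concern holds in a limited form. The primary responder test is not named, and the only candidate in the text is valid but conservative, with maximum size between 1.2% and 2.1% at the 2:1 group sizes examined. At 75% v 10% the avoidable loss is about 4 points if all 30 are analysed, about 8 at 17:9, 12 at 15:7, 15 at 13:7 and 17–19 at 12:6. At 20:10 it reaches about 17 points only under a weaker effect, such as the assumed 50% v 10%. The figures assume that the corrected test would be used for the analysis and that losses stay near 2:1; the last digit depends on the Boschloo convention. This is a worthwhile, cheap improvement to a pilot's analysis, not an invalid analysis.

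**What to change.** In the Statistical Analysis Plan, name Boschloo's exact unconditional test at two-sided 0.05 for the responder comparison. State the two-sided convention (for example, two one-sided tests at 2.5%), and report an exact unconditional confidence interval for the difference in proportions.

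In the Power analysis, replace the printed figures with the exact power of that test at 2:1 under 75% v 10%: about 96% at 20:10, 93% at 17:9, 86% at 15:7, 85% at 13:7 and 77–79% at 12:6. State how many patients are expected in the analysis once carried-forward values are counted.

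Pair the change with one designated primary measure or a multiplicity rule, because the test uses more of the 5% on each endpoint (at most 4.3% v 2.1% at 20:10).

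The cost is a few sentences of wording, with no added patients, visits or data. The test is less familiar than chi-square and needs software with an unconditional exact option.
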